#### 8 METHODOLOGY/STUDY VISITS

#### 8.1 Patient Education

A patient education program will be used as a standard method to educate patients on tenapanor at Screening (Visit 1) and Randomization/Enrollment (Visit 2) and will include the following information:

- Basic information about tenapanor
- How to take tenapanor
- Possible increased bowel movement frequency and/or looser stool with tenapanor, and reason for these potential changes
- What to expect if changes in stool frequency and stool form occur with tenapanor
  - When likely to occur
  - How long likely to last (transient)
  - Severity (mild to moderate)
  - Most patients remain in "normal" range
  - Most patients stay on therapy

The patient education program will also include specific guidance on how to manage the side effect profile of tenapanor and include the following information:

Ensure patient has stopped taking any stool softener, laxative, magnesium, or

23 February 2021 CONFIDENTIAL Page 45 of 60

Protocol Number: TEN-02-402

Edition No. 2

lubricant before starting tenapanor

 Provide recommendation to take Imodium or other over-the-counter anti-diarrheal medicine, if needed

All patient-facing educational materials will be approved by the IRB prior to use.

#### 8.2 Patient Experience Assessment

Patients will be asked about their experience with phosphorus management routine during study compared to before study. The assessment will be conducted via an ePRO questionnaire at Visit 9/Early Termination (end of Part A).

## 8.3 Screening Procedures: Visit 1 (Day -2)

The Investigator will inform each prospective patient of the nature of the study, explain the potential risks, and obtain written informed consent from the patient prior to performing any study-related procedures.

Screening evaluations will consist of the following:

- Assessment of disease status outlined in the inclusion/exclusion criteria
- Date of birth, sex, race, and ethnicity
- Weight (pre-dialysis) and height (kg and cm, respectively)
- Kt/V the most recent value prior to Screening
- Medical and surgical history
- Phosphate binder currently used and prescribed daily dose (must be three times a day)
- Physical examination
- Vital signs (pre-dialysis)
- Electrocardiogram evaluation
- Blood samples for s-P, iFGF23, PTH, clinical laboratory chemistry and hematology tests, and biomarker analysis (pre-dialysis)
- FSH and pregnancy test, if applicable
- eDiary (instructions and beginning of data entry for stool frequency and consistency)
- Prior/concomitant medications; special attention should be given to medications to be discontinued before starting tenapanor (see Appendix I). Any use of PTH-modifying medications in the past 30 days need to be adequately recorded in the Prior/Concomitant Medications eCRF.

23 February 2021 CONFIDENTIAL Page 46 of 60

Protocol Number: TEN-02-402

Edition No. 2

Patient education on information about tenapanor, how to take tenapanor, what they may
experience on tenapanor, medications to be discontinued before starting tenapanor, and
how best to manage a possible increase in bowel movement frequency and/or loose stool
if bothersome (e.g., use of over-the-counter anti-diarrheal), etc

Patients will be instructed not to take any other medications without the approval of the Investigator. Results of the screening evaluations must meet the inclusion/exclusion criteria for the patient to continue in the study.

### 8.4 Treatment Period: Visit 2 (Day 1)

- Inclusion/exclusion criteria (assess s-P criteria using the s-P measurement at Visit 1 and confirm other applicable inclusion/exclusion criteria)
- Randomization (Cohorts 1-2) or enrollment (Cohort 3)
- Medical/surgical history (record only changes to medical history from Visit 1)
- eDiary (instructions and review of data entry for stool frequency and consistency; reinforce the need to complete daily)
- Prior/concomitant medications; special attention should be given to medications to be
  discontinued before starting tenapanor (see Appendix I). Any new PTH-modifying
  medication use or changes to existing PTH-modifying medication use since Screening
  need to be adequately recorded in the Prior/Concomitant Medications eCRF.
- Patient education
- Study drug dispensing
- AE assessment

# 8.5 Treatment Period: Visits 3, 4, 5, 6, 7 and 8 (Days 8, 15, 22, 29, 43, and 57 ± 2 Days)

- Serum phosphorus measurement (pre-dialysis)
- eDiary (review data entry and reinforce the need to complete daily)
- Study drug dispensing and/or return, if applicable
- Concomitant medications; special attention should be given to prohibited concomitant
  medications (see Appendix I). Any new PTH-modifying medication use or changes to
  existing PTH-modifying medication use since the previous assessment of concomitant
  medications need to be adequately recorded in the Prior/Concomitant Medications eCRF.

23 February 2021 CONFIDENTIAL Page 47 of 60

Protocol Number: TEN-02-402

Edition No. 2

AE assessment

## 8.6 End of Treatment Period or Start of Extension Period: Visit 9 (Day $71 \pm 2$ Days)

- Weight (pre-dialysis)
- Physical examination
- Vital signs (pre-dialysis)
- Electrocardiogram evaluation
- Blood samples for s-P, iFGF23, PTH, clinical laboratory chemistry and hematology tests, and biomarker analysis (pre-dialysis)
- Pregnancy test (for women of child-bearing potential)
- Study drug dispensing and/or return, if applicable
- eDiary (review data entry)
- Patient experience assessment
- Concomitant medications; special attention should be given to prohibited concomitant
  medications (see Appendix I). Any new PTH-modifying medication use or changes to
  existing PTH-modifying medication use since the previous assessment of concomitant
  medications need to be adequately recorded in the Prior/Concomitant Medications eCRF.
- AE assessment

## 8.7 Optional Extension Period: Visits 10, 11, and 12 (Days 101, 131, and 161 $\pm$ 7 Days)

- Serum phosphorus measurement (pre-dialysis)
- Study drug dispensing and/or return, if applicable
- Concomitant medications; special attention should be given to prohibited concomitant
  medications (see Appendix I). Any new PTH-modifying medication use or changes to
  existing PTH-modifying medication use since the previous assessment of concomitant
  medications need to be adequately recorded in the Prior/Concomitant Medications eCRF.
- AE assessment

#### 8.8 End of Extension Period: Visit 13 (Day $191 \pm 7$ Days)

- Weight (pre-dialysis)
- Physical examination
- Vital signs (pre-dialysis)

23 February 2021 CONFIDENTIAL Page 48 of 60

Protocol Number: TEN-02-402

Edition No. 2

- Electrocardiogram evaluation
- Blood samples for s-P, iFGF23, PTH, clinical laboratory chemistry and hematology tests, and biomarker analysis (pre-dialysis)
- Pregnancy test (for women of child-bearing potential)
- Study drug return
- Concomitant medications; special attention should be given to prohibited concomitant
  medications (see Appendix I). Any new PTH-modifying medication use or changes to
  existing PTH-modifying medication use since the previous assessment of concomitant
  medications need to be adequately recorded in the Prior/Concomitant Medications eCRF.
- AE assessment

## 8.9 Early Termination Visit

If possible, all assessments and procedures scheduled for Visit 9 (Section 8.6) except study drug dispensing will be completed at the Early Termination visit for patients who prematurely discontinue from the study before Visit 9; those scheduled for Visit 13 (Section 8.8) will be completed at the Early Termination visit for patients who prematurely discontinue from the study between Visit 9 and Visit 13.

#### 8.10 Withdrawal Procedures

In the event of a patient's withdrawal for any reason, every effort will be made to complete the Early Termination visit. At the Early Termination visit, assessments and procedures scheduled for the last scheduled visit in Part A (Visit 9; except study drug dispensing) or Part B (Visit 13) will be performed and are dependent upon whether the patient's withdrawal occurs in Part A or Part B (Section 8.9).

Each withdrawn patient with ongoing AE(s) at study withdrawal will be followed until the AE(s) are resolved or stabilized, the condition becomes chronic in nature, all attempts to determine resolution of the AE(s) are exhausted, or the patient dies.

## 8.11 Criteria for Study Termination

The study may be terminated at any time by the Sponsor for reasons including but not limited to the following: (i) if SAEs occur, (ii) if, in the Sponsor's judgment, there are no further benefits to be achieved from the study, or (iii) for administrative reasons. A site may be closed out if the Investigator does not adhere to the protocol. In the event that the clinical

23 February 2021 CONFIDENTIAL Page 49 of 60

Protocol Number: TEN-02-402

Edition No. 2

development of the investigational product is discontinued, the Sponsor shall inform all Investigators/institutions participating in the study conduct and the IRB overseeing the study.

## 8.12 Total Blood Volume Required for Study

The approximate blood volume required at scheduled visits for each patient is shown in the following table:

**Table 8-1:** Approximate Blood Volume per Patient (Parts A and B Combined)

Test	No. of Samples	Volume Collected for Each Sample (mL)	Total (mL)
Chemistry + FSH	3	7	21
Hematology (blood)	3	3	9
Phosphorus (serum)	12	4	48
PTH (plasma)	3	4	12
iFGF-23 (plasma)	3	4	12
Serum biomarkers	3	5	15
Plasma biomarkers	3	6	18
Total		-	135

#### 8.13 Protocol Deviations

Patients must fully meet the eligibility criteria in order to be enrolled in the study. Ardelyx does not grant protocol waivers to inclusion/exclusion criteria.

A protocol deviation is defined as any intentional or unintentional change to, or noncompliance with, the approved protocol procedures or requirements. Deviations may result from the action or inaction of the patient, the Investigator, or site staff. Examples of deviations include, but are not limited to:

- Enrolling a patient that does not meet study eligibility criteria
- Use of medications, food, drink, herbal remedies, or supplements that are specifically prohibited in the protocol (see Appendix I)
- Missed or out-of-window visits
- Study drug not administered per protocol
- Failure to adhere to the schedule of assessments

23 February 2021 CONFIDENTIAL Page 50 of 60

Protocol Number: TEN-02-402

Edition No. 2

• Failure to comply with regulatory requirements for patient safety

A process for defining and handling protocol deviations will be established for this study. The process will include the definition of "critical" protocol deviation and steps for immediate notification of the "critical" protocol deviation to the Medical Monitor and the Sponsor. The Investigator is responsible for seeing that all known protocol deviations are recorded and handled appropriately.

## 9 STATISTICAL CONSIDERATIONS

## 9.1 Statistical Analysis Plan

A formal SAP will be provided separately. If the language in this protocol and the language in the SAP differ, the SAP governs. Results obtained from the analyses specified in the final approved version of the SAP will become the basis of the clinical study report for this study. Any deviations from the final approved version of the SAP will be documented in the clinical study report.

#### 9.2 Determination of Sample Size

Approximately 300 CKD patients on dialysis and stable phosphate binder therapy will be randomized in a 1:1 ratio to Cohort 1 or Cohort 2 (~150 patients/cohort); and approximately 30 phosphate binder naïve patients with CKD on dialysis will be enrolled into Cohort 3. Overall, approximately 330 patients with CKD on dialysis will be randomized or enrolled in this study. The sample size of this study is not planned based on statistical considerations.

## 9.3 Analysis Populations

The analysis populations defined for this study include: Intent-to-Treat (ITT) population, Safety Population, Full Analysis Set (FAS), and FAS (Cohorts 1-2).

- Intent-to-Treat Population: will be comprised of all randomized or enrolled patients.
- Safety Population: will include all ITT patients who receive at least one dose of study drug. It will be the analysis population for safety and tolerability analyses.
- Full Analysis Set: will include all ITT patients who meet the study entry eligibility
  criteria, receive at least one dose of study drug, and have at least one post-baseline s-P
  measurement during the study. It will be the population used for efficacy analyses.
- Full Analysis Set (Cohorts 1-2): will include all FAS patients in Cohort 1 and Cohort 2. It will be the population used for analyses of efficacy endpoints applicable to Cohort 1 and Cohort 2 only.

23 February 2021 CONFIDENTIAL Page 51 of 60

Protocol Number: TEN-02-402

Edition No. 2

#### 9.4 Statistical Methods

#### 9.4.1 General Considerations

All measures will be summarized descriptively by cohort. Descriptive statistics including the number of observations (n), mean, standard deviation, median, minimum, and maximum will be presented for continuous variables. Summary statistics for iFGF23 will also include geometric mean and geometric coefficient of variation %. Frequency (n) and percent (%) will be presented for categorical variables.

Individual patient data including relevant derived variables will be listed.

Analyses of efficacy endpoints will be performed on the FAS and subsets of FAS. Analyses of safety and tolerability measures will be performed on the Safety population. The statistical testing, if any, will be conducted at a significance level of 0.05 (two-sided).

## 9.4.2 Baseline Descriptive Statistics

Baseline characteristics, including demographics, disease characteristics, prior/concomitant medications, and medical/surgical history will be summarized by cohort and overall for relevant analysis set(s).

## 9.4.3 Efficacy Analysis

All efficacy measures and endpoints will be descriptively summarized at each visit by cohort and for the corresponding analysis set.

For response endpoints, the response rate at each post-baseline visit will be estimated with asymptotic 95% confidence interval for each cohort. For exploratory purposes, inferential analyses may be performed for comparisons of continuous and binary endpoints between cohorts. No multiplicity adjustment will be implemented.

Subgroup analyses by age, sex, race, phosphate binder type, baseline s-P, and ending therapy category (e.g., tenapanor alone, tenapanor  $+ \le 3$  tablets/day phosphate binder, or tenapanor  $+ \le 3$  tablets/day phosphate binder) will also be performed for selective endpoints.

Analyses will be detailed in the SAP.

#### 9.4.4 Handling of Missing Data

Descriptive summaries of efficacy and safety/tolerability measures will be based on observed data. No imputation of missing data will be implemented.

Handling of missing data for inferential analyses will be detailed in the SAP.

23 February 2021 CONFIDENTIAL Page 52 of 60

Protocol Number: TEN-02-402

Edition No. 2

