#### 5.2 Exclusion Criteria

A patient will not be eligible for study participation if he/she meets any of the following exclusion criteria, or will be discontinued at the discretion of the Investigator if he/she develops any of the following medical conditions during the study:

- 1. Severe hyperphosphatemia defined as having an s-P level >10.0 mg/dL at any time point during routine clinical monitoring for the 3 preceding months before Screening (Visit 1).
- 2. Serum/plasma PTH >1200 pg/mL. The most recent value from the patient's medical records should be used.
- 3. Clinical signs of hypovolemia at Screening (Visit 1) as judged by the Investigator.
- 4. History of inflammatory bowel disease or irritable bowel syndrome with diarrhea.
- 5. Scheduled for living donor kidney transplant or plans to relocate to another center during the study.

23 February 2021 CONFIDENTIAL Page 28 of 60

Protocol Number: TEN-02-402

Edition No. 2

6. Use of an investigational agent within 30 days prior to Screening (Visit 1).

- 7. Involvement in the planning and/or conduct of the study (applies to both Ardelyx/Contract Research Organization (CRO) staff and/or staff at the study site).
- 8. If, in the opinion of the Investigator, the patient is unable or unwilling to fulfill the requirements of the protocol or has a condition which would render the results uninterpretable.

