#### 5.3 Patient Withdrawal

Patients are free to discontinue the study at any time, for any reason, and without prejudice to further treatment. The Investigator may remove a patient if, in the Investigator's judgment, continued participation would pose unacceptable risk to the patient or to the integrity of the study data. If possible, all assessments and procedures scheduled for Visit 9 except study drug dispensing will be completed at the Early Termination visit for patients who prematurely discontinue from the study before Visit 9; those scheduled for Visit 13 will be completed at the Early Termination visit for patients who prematurely discontinue from the study between Visit 9 and Visit 13 (Section 8.9 and Section 8.10).

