## 6.1.4 Dose Adjustments

The Investigator may titrate the dose of tenapanor in 10 mg increments down to a minimum of 10 mg QD or up to a maximum of 30 mg BID at any time during the study based on s-P levels and/or GI tolerability.

If a phosphate binder is being taken by a patient in any of the three cohorts, it can be dosed starting at either QD, BID or TID: if taken QD, it should be taken with the largest meal of the day; if taken BID, it should be taken with the same meals tenapanor is taken with. The

23 February 2021 CONFIDENTIAL Page 30 of 60

Protocol Number: TEN-02-402

Edition No. 2

Investigator may decrease the dose of phosphate binder at any time during the study based on s-P levels. However, dose up-titration for phosphate binder is not allowed from Day 1 (Visit 2) until Week 2 of the Treatment Period (Visit 4). Starting from Visit 4, the Investigator may increase the dose of phosphate binder or add phosphate binder based on s-P levels; the dose of a phosphate binder can be titrated up to the maximum dose TID per the corresponding phosphate binder package insert, if needed, based on s-P levels.

If decreasing the dose of tenapanor or phosphate binder due to low s-P levels, the phosphate binder dose should be decreased prior to decreasing the tenapanor dose until patient is no longer taking any phosphate binder. If increasing the dose of tenapanor or phosphate binder due to high s-P levels, the tenapanor dose should be increased prior to increasing the phosphate binder dose until the tenapanor dose reaches 30 mg BID or cannot be increased due to GI tolerability at the Investigator's discretion.

Recommended dose adjustments based on s-P levels during the study are specified below for each cohort:

In Cohort 1 (straight switch to tenapanor),

- If the patient's s-P assessed at or after Visit 4 (Week 2) is >5.5 mg/dL, the Investigator may add one phosphate binder pill daily (QD) (with largest meal) or one phosphate binder pill BID (at same meals as tenapanor). The phosphate binder dosing regimen should start at QD or BID; and the dose of phosphate binder can be titrated up to the maximum dose TID per the corresponding phosphate binder package insert, if needed. When phosphate binder is being added to Cohort 1, the Investigator should use the phosphate binder the patient stopped at the beginning of the study.

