#### 9.4.6 Visit Windows

No analysis visit windows will be formally defined. The schedule of assessments and procedures in Section 1.3 details the intended collection of study variables at specified visits. Data collected at a scheduled visit will be used as the data at the corresponding analysis visit even if the visit is out-of-window. To minimize the amount of missing data, data collected at an unscheduled visit will be mapped to an analysis visit based on analysis windows if data at the corresponding scheduled visit are not available. Similarly, data from the Early Termination visit may also be mapped. Detailed information on analysis windows will be provided in the SAP.

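### By-visit serum phosphorus response rates use observed data only, so a patient who leaves the study in Part A drops out of later denominators; a rate on the full FAS denominator should stand beside them

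*Combined protocol and SAP*

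**What the plan says.** The missing-data rule for descriptive work is in Section 9.4.4: "Descriptive summaries of efficacy and safety/tolerability measures will be based on observed data". The next sentence there rules out imputation. Only the rule for inferential analyses is left to the SAP.

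Section 9.4.3 applies this to the response endpoints: "the response rate at each post-baseline visit will be estimated with asymptotic 95% confidence interval for each cohort". Response at s-P ≤5.5 mg/dL is the first efficacy endpoint in Section 7.5 and corresponds directly to the primary objective in Section 3.1.

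On patients who leave, Section 8.9 says that the Visit 9 assessments "will be completed at the Early Termination visit for patients who prematurely discontinue from the study before Visit 9", where this is feasible. Section 8.10 is firmer and asks sites to try hard to obtain that visit. After it, the only follow-up described is for safety: "Each withdrawn patient with ongoing AE(s) at study withdrawal will be followed until the AE(s) are resolved or stabilized". Section 9.4.6 adds that "data from the Early Termination visit may also be mapped" to an analysis visit, with details deferred to the SAP.

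Three further provisions bear on the point. Section 9.4.1 plans counts with percentages for categorical variables, and patient listings that include derived variables. Section 7.5 lists an endpoint visit for the Treatment Period and one for the whole study, separately from the by-visit summaries, and defines neither. Section 9.3 requires at least one s-P after baseline for entry to the FAS.

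**The concern.** The primary objective asks how many patients reach the phosphorus target when tenapanor is the core therapy. A by-visit rate among patients still being measured answers a narrower question: how many of those who stayed are at target. The two agree only if leavers would have responded at the same rate as the cohort.

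Exits linked to poor phosphorus control are possible. Section 5.3 lets patients stop for any reason, and the investigator may remove a patient where "continued participation would pose unacceptable risk to the patient or to the integrity of the study data". When such a patient goes, a likely non-response leaves both numerator and denominator, and the displayed rate rises without anyone improving. No hypothesis test is planned as primary, so these descriptive rates are the study's result, and their denominator should be plain to the reader.

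**Working it through.** **Is any s-P planned after exit?** Section 7.5 schedules s-P at every visit except Visit 2. There are 13 visits, so 13 − 1 = 12 samples, which equals the 12 phosphorus samples in Table 8-1. That table covers scheduled visits only, so it corroborates the absence of post-exit sampling in Sections 8.9 and 8.10 but does not prove it.

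**Denominator.** The protocol does not write it out. It follows from Sections 9.4.3 and 9.4.4 together: counting an absent patient as a non-responder would be imputation, and that is excluded. One Early Termination value, if mapped, restores the patient at the visit it is mapped to and not at all remaining visits.

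**Size.** The documents give no discontinuation or response rate and no power calculation to reproduce (Section 9.2 says the sample size has no statistical basis). The inputs are:

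- n = 150 per cohort: the planned number in Section 9.2, taken as the FAS size (assumption)
- p: response rate if nobody were lost, 30%, 50% or 70% (assumption)
- k: patients absent at a visit, 5 or 15 (assumption)
- q: share of those k who would have responded, 0, 25% or 60% (assumption)

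Observed rate = (np − kq)/(n − k). Shift from p = k(p − q)/(n − k).

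Worked case, k = 15, q = 0, p = 50%: 15 × 0.50/135 = 0.0556, or +5.6 points.

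| k | q | p = 30% | p = 50% | p = 70% |
|---|---|---|---|---|
| 5 | 0 | +1.0 | +1.7 | +2.4 |
| 5 | 25% | +0.2 | +0.9 | +1.6 |
| 5 | 60% | −1.0 | −0.3 | +0.3 |
| 15 | 0 | +3.3 | +5.6 | +7.8 |
| 15 | 25% | +0.6 | +2.8 | +5.0 |
| 15 | 60% | −3.3 | −1.1 | +1.1 |

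For scale, the 95% half-width 1.96·√(p(1 − p)/150) is 7.3, 8.0 and 7.3 points at the three values of p.

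**What a full denominator shows.** Take an observed rate of 40% at a visit. The upper bound counts every leaver as a responder.

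- 10% lost: 54/135 = 40%, against 54/150 = 36%; upper bound 69/150 = 46%.
- 20% lost: 48/120 = 40%, against 48/150 = 32%; upper bound 78/150 = 52%.
- 30% lost: 42/105 = 40%, against 42/150 = 28%; upper bound 87/150 = 58%.

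**The composite is not a bias correction.** It equals (np − kq)/n and so lies below p by kq/n. At k = 15 that is 0, 2.5 and 6.0 points for q = 0, 25% and 60%. It measures a different quantity, being on study and at target.

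**The case against.** The strongest reply is that much of this is already visible or may be handled elsewhere. Counts and listings are planned, so a reader who divides the by-visit responder count by the FAS size gets nearly the composite rate. Visits 9 and 13 are already post-baseline visits, so the separately named endpoint visits are plausibly something else, perhaps a last-value summary that keeps early leavers. Section 9.1 makes the separate SAP govern, and that SAP is not in the supplied text. Section 9.4.6 aims to limit missing data. The size is pure assumption: of the 18 scenarios above, the sign reverses in 4, and only one shift (+7.8 against 7.3) exceeds its half-width. The study is open-label Phase 4 and descriptive.

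Most of this stands as a limit on weight. It does not remove the point. The endpoint visit is undefined in the text, the mapping is optional, and the descriptive rule is stated in the protocol itself.

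A reader might also infer stronger things that the documents do not support:

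- **That the observed rate is biased upward.** The direction depends on whether q is below p, which no section shows.
- **That patients with very high on-study s-P are removed as failures.** The lead-in to Section 5.2 says a patient "will be discontinued at the discretion of the Investigator if he/she develops any of the following medical conditions during the study", but item 1 describes values from the three months before Screening. On-study elevation is managed under Section 6.1.4: "Starting from Visit 4, the Investigator may increase the dose of phosphate binder or add phosphate binder based on s-P levels".
- **That the comparison of Cohorts 1 and 2 is distorted.** Cohort 1 stops all binder on Day 1 and Cohort 2 keeps up to half, so losses could differ, but nothing shows that they will. With 15 against 5 lost, q = 0 and equal p, the artificial difference is 2.3, 3.8 or 5.4 points, against half-widths of 10.4, 11.3 and 10.4 for the difference, from 1.96·√(2p(1 − p)/150).
- **That stopping tenapanor ends s-P collection.** Section 7.4.1 records drug withdrawal separately from study discontinuation. The gap concerns patients who leave the study.

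**Conclusion.** The point holds for the by-visit s-P response rates in Part A. On the protocol's own rules, a patient who leaves the study is absent from later visit denominators unless an Early Termination value is mapped there. If leavers would have responded less often than the cohort, the observed rate is too high by k(p − q)/(n − k). This rests on an assumed FAS of 150 per cohort and on assumed loss and response rates, because the documents give none.

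The mechanism is clear from the text; the size and sign are not. No by-visit rate is designated primary, and no power or alpha claim is affected. The consequence is minor to moderate, and the remedy is worth making because it is cheap.

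**What to change.** In Sections 9.4.3 and 9.4.4, and in the SAP, add for each Part A visit a second response rate beside the observed-data rate:

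- The denominator is all FAS patients in the cohort.
- Patients who have left the study and have no s-P at that visit count as non-responders.
- The rate is labelled a composite (on study and s-P ≤5.5 mg/dL), so that it is not read as a corrected version of the observed rate.

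In the same table, show by cohort the number of on-study patients with a missed s-P, with one stated rule for them, and the number of treated patients outside the FAS because they have no post-baseline s-P, since neither rate includes them. Limit the composite to Part A, because Part B is optional and not entering it is not a failure.

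The cost is one extra table from data already collected, and a rate that may look slightly less favourable. No planned analysis is replaced.
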